3.3 Inclusion of Women and Minorities

Both men and women of all races and ethnic groups are eligible for this trial.

4. REGISTRATION PROCEDURES

4.1 General Guidelines for DF/HCC Institutions

Institutions will register eligible participants in the Clinical Trials Management System (CTMS) OnCore. Registrations must occur prior to the initiation of protocol therapy. Any participant not registered to the protocol before protocol therapy begins will be considered ineligible and registration will be denied.

An investigator will confirm eligibility criteria and a member of the study team will complete the protocol-specific eligibility checklist.

Following registration, participants may begin protocol therapy. Issues that would cause treatment delays should be discussed with the Overall Principal Investigator (PI). If a participant does not receive protocol therapy following registration, the participant's registration on the study must be canceled. Registration cancellations must be made in OnCore as soon as possible.

4.2 Registration Process for DF/HCC Institutions

DF/HCC Standard Operating Procedure for Human Participant Research Titled Centralized Participant Registration (SOP #: REGIST-101A) or Decentralized Participant Registration (SOP #: REGIST-101B) must be followed.

5. TREATMENT PLAN

5.1 Treatment Regimen

This is a prospective trial which will accrue participants with solid tumors to evaluate the safety, clinical, and immunological effect of the combination of pembrolizumab and trebananib. The treatment will include an induction phase of pembrolizumab and trebananib for 4 cycles (12 wks) followed by pembrolizumab alone for up to 2 years. This trial will be conducted in 2 parts:

Part I will use a standard 3+3 dose escalation design in all solid tumors (refer to Table 2. Dose escalation will begin in dose cohort +1 (refer to Table 3). If two or more patients in dose cohort +1 experience a DLT, the next cohort of patients will be enrolled into dose cohort -1. Should dose cohort -1 prove too toxic (i.e. two or more patients experience a DLT), enrollment to the study will stop. If the toxicity profile of dose cohort +1 is acceptable per the escalation decision rules in Table 2, the next cohort will be enrolled into dose cohort +2. Should dose cohort +2 have acceptable toxicity per the escalation decision rules in Table 2, that will be the RP2D; otherwise, dose cohort +1 will be the RP2D.

Table 2. Dose Escalation Schema

Number of Patients with DLT at a Given Dose Level	Escalation Decision Rule
0 out of 3	Enter 3 patients at the next dose level.
≥ 2	Dose escalation will be stopped. This dose level will be declared the maximally administered dose (highest dose administered). Three (3) additional patients will be entered at the next lowest dose level if only 3 patients were treated previously at that dose.
1 out of 3	Enter 3 more patients at this dose level. 
 • If 0 of these 3 patients experience DLT, proceed to the next dose level. • If 1 or more of this group suffer DLT, then dose escalation is stopped, and this dose is declared the maximally administered dose. Three (3) additional patients will be entered at the next lowest dose level if only 3 patients were treated previously at that dose.
≤ 1 out of 6 at highest dose level below the maximally administered dose	This is generally the recommended phase 2 dose. At least 6 patients must be entered at the recommended phase 2 dose.

Table 3. Part I Dose Escalation Schedule

Dose Cohort	Pembrolizumab every 3 weeks IV	Trebananib weekly IV	N
- 1	200mg	3 mg/kg	3+3
+1	200mg	15 mg/kg	3+3
+2	200mg	30 mg/kg	3+3

Part II has four dose expansion cohorts to be treated at the RP2D of pembrolizumab and trebananib: melanoma (closed to accrual), renal cell carcinoma (closed to accrual), ovarian cancer, and colorectal cancer. For ovarian cancer, 12 patients will be enrolled and treated. For CRC patients, a total of 37 patients will be enrolled on the expansion cohort. For the RCC cohort, 4 patients were enrolled and treated in the expansion cohort.

The investigator shall take responsibility for and shall take all steps to maintain appropriate records and ensure appropriate supply, storage, handling, distribution and usage of trial treatments in accordance with the protocol and any applicable laws and regulations.

5.2 Trial Treatments

The treatment to be used in this trial is outlined below in Table 4. Each treatment cycle will be 3 weeks (21 days) long.

The treatment will include an induction phase of pembrolizumab and trebananib for 4 cycles (12 wks) followed by pembrolizumab alone for 2 years.

Table 4. Regimen Description for Parts I and II

Regimen Description					
Agent	Pre-medications	Dose	Route	Schedule ***	Cycle Length
Pembrolizumab	Not routinely necessary unless prior infusion reaction	200mg at a final concentration of 1 mg/mL to 10 mg/mL in NS or D5	IV over approximately 30 minutes (range: 25-40 minutes)	Day 1	21 days (3 weeks)
Trebananib	Not routinely necessary unless prior infusion reaction	** mg/kg at a final concentration of 30mg/mL in NS	****IV over approximately 30 minutes	Day 1,8,15	
**Doses as appropriate for assigned dose level.					
*** The treatment will include an induction phase of pembrolizumab and trebananib for 4 cycles (12 wks) followed by pembrolizumab alone for 2 years.					

**** First dose of trebananib should be administered over 60 minutes.

5.2.1 Dose Selection/Modification

5.2.1.1 Dose Selection

The rationale for selection of doses to be used in this trial is provided in Section 2.3.2

Details on the preparation and administration of pembrolizumab and trebananib are provided in the pharmacy manual.

5.3 Agent Administration

Treatment will be administered on an outpatient basis. Dose for weight-based drugs should be flagged for recalculation at the start of each cycle should the weight of a participant change by more than 5% from the previous cycle's Day 1 weight. No investigational or commercial agents or therapies other than those described below may be administered with the intent to treat the patient's malignancy.

5.3.1 Timing of Dose Administration: Pembrolizumab

Pembrolizumab should be administered on Day 1 of each cycle after all procedures/assessments have been completed as detailed on the Trial Flow Chart (Section 9). Pembrolizumab may be administered with trebananib up to 2 days before or after the scheduled Day 1 of each cycle due to administrative reasons. Pembrolizumab will be administered before trebananib.

Pembrolizumab 200 mg will be administered as a 30 minute IV infusion every 3 weeks. Sites should make every effort to target infusion timing to be as close to 30 minutes as possible. However, given the variability of infusion pumps from site to site, a window of -5 minutes and +10 minutes is permitted (i.e., infusion time is 30 minutes: -5 min/+10 min).

The Pharmacy Manual contains specific instructions for the preparation of the pembrolizumab infusion fluid and administration of infusion solution.

5.3.2 Timing of Dose Administration: Trebananib

Trebananib should be administered on Day 1, 8, and 15 of each 21-day cycle after all procedures/assessments have been completed. Trebananib may be administered with pembrolizumab up to 2 days before or after the scheduled Day of each cycle due to administrative reasons (± 2 days).

The first dose of trebananib will be administered by IV infusion over a 60-minute period. If the initial dose administration is well tolerated, future administrations may be given over approximately 30 minutes (treatment cycle intervals may be increased due to toxicity as described in section 5). A window of -5 to +10 minutes is permitted (i.e. infusion time is 30 minutes: -5 min/+10 min). Trebananib will be administered within 2 hours after Pembrolizumab.

The Investigational Product Instruction Manual (IPIM) contains specific instructions for the preparation of the trebananib infusion fluid and administration of infusion solution.

5.3.3 Dose Modifications

5.3.3.1 Pembrolizumab Dose Modification and Toxicity Management for Immune-Related AEs Associated with Pembrolizumab and Combination Therapy

AEs associated with pembrolizumab exposure, including coadministration with additional compounds, may represent an immunologic etiology. These immune-related AEs (irAEs) may occur shortly after the first dose or several months after the last dose of pembrolizumab/combination treatment and may affect more than one body system simultaneously. Therefore, early recognition and initiation of treatment is critical to reduce complications. Based on existing clinical study data, most irAEs were reversible and could be managed with interruptions of pembrolizumab/combination treatment, administration of corticosteroids and/or other supportive care. For suspected irAEs, ensure adequate evaluation to confirm etiology or exclude other causes. Additional procedures or tests such as bronchoscopy, endoscopy, skin biopsy may be included as part of the evaluation. Dose modification and toxicity management guidelines for irAEs associated with pembrolizumab/combination treatment are provided in Table 5.. See Section 5.9 for supportive care guidelines, including use of corticosteroids.

Attribution of Toxicity:

When study interventions are administered in combination, attribution of an adverse event to a single component is likely to be difficult. Therefore, while the investigator may attribute a toxicity event [to the combination, to [trebananib alone] or to pembrolizumab alone], for adverse events listed in Table 5, both interventions must be held according to the criteria in Table 5 Dose Modification and Toxicity Management Guidelines for Immune-Related Adverse Events Associated with Pembrolizumab.

Holding Study Interventions:

When study interventions are administered in combination, if the AE is considered immune-related, both interventions should be held according to the recommended dose modifications.

Restarting Study Interventions:

Participants may not have any dose modifications (no change in dose or schedule) of pembrolizumab in this study, as described in Table 5.

- If the toxicity does not resolve or the criteria for resuming treatment are not met, the participant must be discontinued from all study interventions
- If the toxicities do not resolve and conditions are aligned with what is defined in Table 5, the combination of trebananib and pembrolizumab may be restarted at the discretion of the

investigator. [In these cases where the toxicity is attributed to the combination of trebananib and pembrolizumab or trebananib alone, re-initiation of pembrolizumab as a monotherapy may be considered at the principal investigator's discretion.]

Table 5 Dose modification and toxicity management guidelines for immune-related AEs associated with pembrolizumab monotherapy and IO combinations

General instructions:

1. Severe and life-threatening irAEs should be treated with IV corticosteroids followed by oral steroids. Other immunosuppressive treatment should begin if the irAEs are not controlled by corticosteroids.
2. Study intervention must be permanently discontinued if the irAE does not resolve or the corticosteroid dose is not ≤ 10 mg/day within 12 weeks of the last study intervention treatment.
3. The corticosteroid taper should begin when the irAE is \leq Grade 1 and continue at least 4 weeks.
4. If study intervention has been withheld, study intervention may resume after the irAE decreased to \leq Grade 1 after corticosteroid taper.

irAEs	Toxicity Grade (CTCAE v5.0)	Action With Pembrolizumab	Corticosteroid and/or Other Therapies	Monitoring and Follow-up
Pneumonitis	Grade 2	Withhold	
 • Administer corticosteroids (initial dose of 1 to 2 mg/kg prednisone or equivalent) followed by taper • Add prophylactic antibiotics for opportunistic infections 	
 • Monitor participants for signs and symptoms of pneumonitis • Evaluate participants with suspected pneumonitis with radiographic imaging and initiate corticosteroid treatment
	Recurrent Grade 2, Grade 3 or 4	Permanently discontinue		
Diarrhea/Colitis	Grade 2 or 3	Withhold	
 • Administer corticosteroids (initial dose of 1 to 2 mg/kg prednisone or equivalent) followed by taper 	
 • Monitor participants for signs and symptoms of enterocolitis (ie, diarrhea, abdominal pain, blood or mucus in stool with or without fever) and of bowel perforation (ie, peritoneal signs and ileus) • Participants with \geq Grade 2 diarrhea suspecting colitis should consider GI consultation and performing endoscopy to rule out colitis
	Recurrent Grade 3 or Grade 4	Permanently discontinue		

irAEs	Toxicity Grade (CTCAE v5.0)	Action With Pembrolizumab	Corticosteroid and/or Other Therapies	Monitoring and Follow-up
				
 Participants with diarrhea/colitis should be advised to drink liberal quantities of clear fluids. If sufficient oral fluid intake is not feasible, fluid and electrolytes should be substituted via IV infusion
AST or ALT Elevation or Increased Bilirubin	Grade 2 ^a	Withhold	
 Administer corticosteroids (initial dose of 0.5 to 1 mg/kg prednisone or equivalent) followed by taper 	
 Monitor with liver function tests (consider weekly or more frequently until liver enzyme value returned to baseline or is stable)
	Grade 3 ^b or 4 ^c	Permanently discontinue	
 Administer corticosteroids (initial dose of 1 to 2 mg/kg prednisone or equivalent) followed by taper 	
T1DM or Hyperglycemia	New onset T1DM or Grade 3 or 4 hyperglycemia associated with evidence of β -cell failure	Withhold ^d	
 Initiate insulin replacement therapy for participants with T1DM Administer antihyperglycemic in participants with hyperglycemia 	
 Monitor participants for hyperglycemia or other signs and symptoms of diabetes
Hypophysitis	Grade 2	Withhold	
 Administer corticosteroids and initiate hormonal replacements as clinically indicated 	
 Monitor for signs and symptoms of hypophysitis (including hypopituitarism and adrenal insufficiency)
	Grade 3 or 4	Withhold or permanently discontinue ^d		
Hyperthyroidism	Grade 2	Continue		

irAEs	Toxicity Grade (CTCAE v5.0)	Action With Pembrolizumab	Corticosteroid and/or Other Therapies	Monitoring and Follow-up
	Grade 3 or 4	Withhold or permanently discontinue ^d	
 Treat with nonselective beta-blockers (eg, propranolol) or thionamides as appropriate 	
 Monitor for signs and symptoms of thyroid disorders
Hypothyroidism	Grade 2, 3 or 4	Continue	
 Initiate thyroid replacement hormones (eg, levothyroxine or liothyronine) per standard of care 	
 Monitor for signs and symptoms of thyroid disorders
Nephritis: grading according to increased creatinine or acute kidney injury	Grade 2	Withhold	
 Administer corticosteroids (prednisone 1 to 2 mg/kg or equivalent) followed by taper 	
 Monitor changes of renal function
	Grade 3 or 4	Permanently discontinue		
Neurological Toxicities	Grade 2	Withhold	
 Based on severity of AE administer corticosteroids 	
 Ensure adequate evaluation to confirm etiology and/or exclude other causes
	Grade 3 or 4	Permanently discontinue		
Myocarditis	Grade 1	Withhold	
 Based on severity of AE administer corticosteroids 	
 Ensure adequate evaluation to confirm etiology and/or exclude other causes
	Grade 2, 3 or 4	Permanently discontinue		
Exfoliative Dermatologic Conditions	Suspected SJS, TEN, or DRESS	Withhold	
 Based on severity of AE administer corticosteroids 	
 Ensure adequate evaluation to confirm etiology or exclude other causes
	Confirmed SJS, TEN, or DRESS	Permanently discontinue		
All Other irAEs	Persistent Grade 2	Withhold	
 Based on severity of AE administer corticosteroids 	
 Ensure adequate evaluation to confirm etiology or exclude other causes
	Grade 3	Withhold or discontinue based on the event ^e		
	Recurrent Grade 3 or Grade 4	Permanently discontinue		

AE(s)=adverse event(s); ALT= alanine aminotransferase; AST=aspartate aminotransferase; CTCAE=Common Terminology Criteria for Adverse Events; DRESS=Drug Rash with Eosinophilia and Systemic Symptom; GI=gastrointestinal; IO=immuno-oncology; ir=immune related; IV=intravenous; SJS=Stevens-Johnson Syndrome; T1DM=type 1 diabetes mellitus; TEN=Toxic Epidermal Necrolysis; ULN=upper limit of normal.

Note: Non-irAE will be managed as appropriate, following clinical practice recommendations.

irAEs	Toxicity Grade (CTCAE v5.0)	Action With Pembrolizumab	Corticosteroid and/or Other Therapies	Monitoring and Follow-up
^a	AST/ALT: >3.0 to 5.0 x ULN if baseline normal; >3.0 to 5.0 x baseline, if baseline abnormal; bilirubin: >1.5 to 3.0 x ULN if baseline normal; >1.5 to 3.0 x baseline if baseline abnormal			
^b	AST/ALT: >5.0 to 20.0 x ULN, if baseline normal; >5.0 to 20.0 x baseline, if baseline abnormal; bilirubin: >3.0 to 10.0 x ULN if baseline normal; >3.0 to 10.0 x baseline if baseline abnormal			
^c	AST/ALT: >20.0 x ULN, if baseline normal; >20.0 x baseline, if baseline abnormal; bilirubin: >10.0 x ULN if baseline normal; >10.0 x baseline if baseline abnormal			
^d	The decision to withhold or permanently discontinue pembrolizumab is at the discretion of the investigator or treating physician. If control achieved or ≤ Grade 2, pembrolizumab may be resumed.			
^e	Events that require discontinuation include, but are not limited to: encephalitis and other clinically important irAEs (eg, vasculitis and sclerosing cholangitis).			

Dose modification and toxicity management of infusion-reactions related to pembrolizumab

Pembrolizumab may cause severe or life-threatening infusion-reactions including severe hypersensitivity or anaphylaxis. Signs and symptoms usually develop during or shortly after drug infusion and generally resolve completely within 24 hours of completion of infusion. Dose modification and toxicity management guidelines on pembrolizumab associated infusion reaction are provided in Table 6.

Table 6. Pembrolizumab Infusion Reaction Dose Modification and Treatment Guidelines

NCI CTCAE Grade	Treatment	Premedication at subsequent dosing
Grade 1 Mild reaction; infusion interruption not indicated; intervention not indicated	Increase monitoring of vital signs as medically indicated until the participant is deemed medically stable in the opinion of the investigator.	None
Grade 2 Requires therapy or infusion interruption but responds promptly to symptomatic treatment (e.g., antihistamines, NSAIDs, narcotics, IV fluids); prophylactic medications indicated for < =24 hrs	
Stop Infusion .
 
Additional appropriate medical therapy may include but is not limited to:
 
 IV fluids Antihistamines NSAIDS Acetaminophen Narcotics 
Increase monitoring of vital signs as medically indicated until the participant is deemed medically stable in the opinion of the investigator.
 
If symptoms resolve within one hour of stopping drug infusion, the infusion may be restarted at 50% of the original infusion rate (e.g., from 100 mL/hr to 50 mL/hr). Otherwise dosing will be held until symptoms resolve and the participant should be premedicated for the next scheduled dose.
 
Participants who develop Grade 2 toxicity despite adequate premedication should be permanently discontinued from further study drug intervention.
	
Participant may be premedicated 1.5h (± 30 minutes) prior to infusion of pembrolizumab with:
 
Diphenhydramine 50 mg po (or equivalent dose of antihistamine).
 
Acetaminophen 500-1000 mg po (or equivalent dose of analgesic).

NCI CTCAE Grade	Treatment	Premedication at subsequent dosing

Grades 3 or 4
 
Grade 3: Prolonged (i.e., not rapidly responsive to symptomatic medication and/or brief interruption of infusion); recurrence of symptoms following initial improvement; hospitalization indicated for other clinical sequelae (e.g., renal impairment, pulmonary infiltrates)
 
Grade 4: Life-threatening; pressor or ventilatory support indicated
	
Stop Infusion. Additional appropriate medical therapy may include but is not limited to:
 
 IV fluids Antihistamines NSAIDS Acetaminophen Narcotics Oxygen Pressors Corticosteroids Epinephrine** 
Increase monitoring of vital signs as medically indicated until the participant is deemed medically stable in the opinion of the investigator. Hospitalization may be indicated. ** In cases of anaphylaxis, epinephrine should be used immediately.
 
Participant is permanently discontinued from further trial treatment administration.
	No subsequent dosing

Appropriate resuscitation equipment should be available at the bedside and a physician readily available during the period of drug administration. For further information, please refer to the Common Terminology Criteria for Adverse Events v5.0 (CTCAE) at http://ctep.cancer.gov.
		

Other allowed dose interruption for pembrolizumab

Pembrolizumab may be interrupted for situations other than treatment-related AEs such as medical/surgical events and/or unforeseen circumstances not related to study intervention. However, intervention is to be restarted within 3 weeks of the originally scheduled dose and within 42 days of the previously administered dose, unless otherwise discussed with the Sponsor. The reason for study intervention interruption should be documented in the patient's study record.

If pembrolizumab is held or treatment delayed, trebananib should also be delayed such that the two drugs are administered on the same day. If pembrolizumab is to be permanently discontinued, the patients may continue trebananib treatment alone.

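### Section 5.3.3.2 lets pembrolizumab continue after a trebananib-attributed Grade 3–4 liver or kidney event for which Table 5 requires a permanent stop whatever the attribution

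*Combined protocol and SAP*

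**What the plan says.** Section 5.3.3.1, under Attribution of Toxicity, accepts that with two drugs "attribution of an adverse event to a single component is likely to be difficult". It foresees that "the investigator may attribute a toxicity event [to the combination, to [trebananib alone] or to pembrolizumab alone", and then takes away the effect of that judgement: "for adverse events listed in Table 5, both interventions must be held according to the criteria in Table 5".

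Two Table 5 rows matter here: "AST or ALT Elevation or Increased Bilirubin" and "Nephritis: grading according to increased creatinine or acute kidney injury". In both, the action at Grade 3 or 4 is permanent discontinuation of pembrolizumab. Footnote b defines Grade 3 for the liver row as "AST/ALT: >5.0 to 20.0 x ULN, if baseline normal" and "bilirubin: >3.0 to 10.0 x ULN if baseline normal".

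Section 5.3.3.2 has two general rules for trebananib:

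- For Grade 3–4 toxicities that it has not already listed and that are related to trebananib or the combination, trebananib is held until Grade 1 or baseline and resumed one dose level lower.
- For a toxicity judged related to trebananib and not to pembrolizumab, pembrolizumab may go on once the toxicity is Grade 1 or resolved.

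Neither rule mentions Table 5 or immune-related events.

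Section 5.12 lists unacceptable adverse events that end protocol therapy. One line covers Grade 3 drug-related autoimmune or inflammatory events, with examples. A separate line on liver tests names only Grade 4 AST or ALT.

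**The concern.** A site that follows Section 5.3.3.2 could give pembrolizumab again after a possibly immune-related Grade 3 liver or kidney event, while a site that follows Section 5.3.3.1 must stop it for good. The difference would rest on a single-drug attribution that the protocol itself regards as unreliable.

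The stakes are first patient safety. Trebananib ends after 4 cycles, but pembrolizumab is planned for 24 months or 35 administrations, whichever is later, so 35 − 4 = 31 of those 35 doses fall after induction. Consistency is also at stake: the Part 2 primary objective in Section 1.2 is the safety and tolerability of the combination, and the same event could be managed, and appear in the discontinuation data, in two ways.

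**Working it through.** The plan gives no figure to reproduce, and no arithmetic decides the point. The check is a comparison of rules for one case: a Grade 3 AST/ALT or bilirubin rise, or Grade 3 nephritis, that may be immune-related, is attributed to trebananib alone, and later returns to Grade 1.

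**Step 1: do both sections reach this case?** Yes. The events are rows of Table 5, and Section 5.3.3.1 applies Table 5 even on a trebananib-only attribution. The toxicities that Section 5.3.3.2 lists individually include nephrotic syndrome and thrombotic microangiopathy, but not liver-test elevation or nephritis. These therefore fall under its general rules.

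**Step 2: what does each require?**

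| Source | Pembrolizumab | Trebananib |
|---|---|---|
| 5.3.3.1 with Table 5 | Permanent stop | Stopped: the first restart bullet ends all study interventions when the criteria for resuming are not met |
| 5.3.3.2 | May continue at Grade 1 | Resumes one level lower; at the 30 mg/kg RP2D this is 15 mg/kg (Table 3) |
| 5.12, liver line | Requires no stop below Grade 4 AST or ALT | Same |
| 5.12, Grade 3 autoimmune or inflammatory line | Stop, if its examples are read as open-ended | Same |

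The first two rows cannot both be followed.

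**Step 3: does any other text settle precedence?**

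- Section 5.4 confines its own resumption criteria to events that are not autoimmune or inflammatory. Section 5.3.3.2 carries no such limit.
- Section 5.3.3.1, under Restarting Study Interventions, has a bracketed option to restart pembrolizumab alone, at the principal investigator's discretion, when the combination or trebananib alone is blamed. It is tied to Table 5 conditions being met, so on a plain reading it does not lift a permanent stop. But the bullet leading into it begins, like the bullet before it, with toxicities that have not resolved, and then permits a restart. This looks like a drafting slip, and a site could take it as support for Section 5.3.3.2.
- Section 5.12 is not a safe tie-breaker, because it also departs from Table 5 in the opposite direction: it discontinues for Grade 3 colitis, where Table 5 withholds at first occurrence.

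**Step 4: how wide is the liver mismatch?** With a normal baseline, Table 5 stops pembrolizumab above 5 × ULN for AST/ALT and above 3 × ULN for bilirubin. The Section 5.12 liver line starts at Grade 4 AST/ALT, above 20 × ULN (footnote c), and does not mention bilirubin. The Grade 3 band between the two is AST/ALT above 5 and up to 20 × ULN, and bilirubin above 3 and up to 10 × ULN. Grade 4 bilirubin is not named either.

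**The case against.** The best defence is that the two rules govern different events. Table 5 concerns immune-related events associated with pembrolizumab, and its note leaves other events to clinical practice. Section 5.10.1 says the treatment guidance applies when the event is judged related to pembrolizumab and need not be followed otherwise. On that reading, Section 5.3.3.2 deals only with non-immune trebananib toxicity.

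This holds for events that are clearly not immune-related, and no conflict is claimed for them. It does not dispose of the rest. Section 5.10.1 still refers dose modification to Table 5. And if a trebananib-only attribution took an event out of Table 5, the attribution sentence in Section 5.3.3.1 would have nothing to do.

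A second defence is that Section 5.12 catches the cases anyway through its Grade 3 autoimmune or inflammatory line. That is a reasonable reading of an illustrative list, and it narrows the gap. It does not close it, because the same list has a specific liver line with a higher threshold.

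A third is that the reach is small: the site must attribute the event to trebananib alone, wait for recovery to Grade 1, and prefer a permissive rule in the trebananib section to a mandatory one in the pembrolizumab section. This stands, and it limits the size of the point.

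**Conclusion.** The conflict holds for events listed in Table 5 that are or may be immune-related, are attributed to trebananib alone, and recover to Grade 1. For Grade 3–4 AST/ALT or bilirubin elevation and Grade 3–4 nephritis, one section requires a permanent stop of pembrolizumab and another allows it to continue. The liver threshold in Section 5.12 is a separate and smaller mismatch. The documents give no rate for these events on the combination, so no number of patients can be stated. The correction should be made because it concerns re-exposure after a serious event and costs almost nothing.

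Two stronger readings are not supported.

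- A reader might infer that the plan leaves open whether a permanent Table 5 stop also ends trebananib, because it says "If pembrolizumab is to be permanently discontinued, the patients may continue trebananib treatment alone". That sentence sits under interruptions for reasons other than treatment-related adverse events, and the restart bullets in Section 5.3.3.1 end all study interventions when the criteria for resuming are not met.
- A reader might count five Table 5 rows with a permanent stop at a first Grade 3 event (pneumonitis, liver tests, nephritis, neurological toxicities, myocarditis), find two of them (pneumonitis and neurologic events) named in the Section 5.12 line, and conclude that 5 − 2 = 3 are uncovered. They are unnamed, but the list gives examples, so that count is not a count of gaps.

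**What to change.** Make three wording changes.

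1. In Section 5.3.3.2, state that the general Grade 3–4 rule and the trebananib-only attribution rule do not apply to Table 5 events that are or may be immune-related, and that for these the Table 5 action governs regardless of attribution.
2. In Section 5.3.3.1, remove the negation from the second restart bullet so that it applies when the toxicities have resolved. State that the bracketed pembrolizumab-alone restart is not available where Table 5 says to discontinue permanently. Without this, the first change would leave an attribution-based route open inside Section 5.3.3.1.
3. In Section 5.12, align the liver line with Table 5 for immune-related events: Grade 3 or 4 AST, ALT or bilirubin requires discontinuation. Section 5.12 criteria end protocol therapy as a whole, which agrees with the first restart bullet in Section 5.3.3.1.

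The cost is amendment text only: no extra patients, visits, data fields or analyses. Participants who might have continued under Section 5.3.3.2 would stop, as Section 5.3.3.1 with Table 5 already requires.
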